17.1.1. ALL TEAEs

Incidence of TEAEs will be presented for each treatment period by System Organ Class (SOC) and Preferred Term (PT) and also broken down further by maximum severity and relationship to study medication.

17.1.1.1. Severity

Severity is classed according to CTCAE v4.03 - Grade 1/mild, Grade 2/moderate, Grade 3/severe, Grade 4/ life-threatening, or Grade 5/Fatal. TEAEs starting after the first dose of study medication with a missing severity will be classified as Grade3/severe. If a patient reports a TEAE more than once within that SOC/ PT/Treatment period, the AE with the highest severity grade will be used in the corresponding severity summaries.

17.1.1.2. Relationship to Study Medication

Relationship, as indicated by the Investigator, is classed as " Unrelated/not related", "Unlikely related" "possibly related", "probably related" and "definitely related" (increasing severity of relationship). A "related" TEAE is defined as a TEAE with a relationship to study medication as "possibly related", "probably related" and "definitely related" to study medication. TEAEs with a missing relationship to study medication will be regarded as "possible related" to study medication. If a patient reports the same AE more than once within that SOC/ PT/Treatment period, the AE with the worst case relationship to study medication will be used in the corresponding relationship summaries.

All AEs, with the causal relationship to the trial drug reported as "possible", "probable" or "definite" will be considered ADRs. If the relationship to the trial drug is not given, then the AE must be treated as if the relationship were "possible."

17.1.1.3. Adverse Drug Reaction

All noxious and unintended responses to an investigational product related to any dose of the investigation products should be considered adverse drug reactions (ADRs). The phrase "responses to an investigational product" means that a causal relationship between an investigational product and an AE is at least a reasonable possibility. All AEs judged by either the reporting investigator or the sponsor as having a reasonable causal relationship to an investigational product will be designated as ADRs.

All AEs, with the causal relationship to the trial drug reported as "possible", "probable" or "definite" will be considered ADRs. If the relationship to the trial drug is not given, then the AE must be treated as if the relationship were "possible."

If a patient reports the same AE more than once within that SOC/ PT, the AE with the worst case relationship to

Document:	\\JEEDC-NAS01A\Biosdata\Mylan\INSULIN_GLARGINE\UXA25824\Biostatistics\Documentation\SAP	Version Number:	Final V1.0
Author:	[name] and [name]	Version Date:	[27JUL2016]

Template No: CS_TP_BS016 – Revision 3
Effective Date: 01May2012

Reference: CS_WI_BS005

study medication will be used in the corresponding relationship summaries.

Frequency and percentage of patients having adverse drug reactions will be presented by treatment sequence group, treatment period, SOC and PT.

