#### ***9.9.4. Adverse Event Analyses***

The evaluation of adverse events will include assessments of TEAEs and SAEs.

The incidence of TEAEs will be summarized to include only one occurrence of a PT per patient per treatment period. If a patient reports multiple occurrences of the same PT and treatment period, then that PT will only be counted once. As with the PT, if a patient reports multiple TEAEs within the same SOC and treatment period, that SOC will only be counted once. Incidence of TEAEs will be presented by treatment sequence. The incidence of TEAE by severity and relation to study drug will also be summarized by treatment sequence. The incidence of both local and systemic allergic reaction-related TEAEs will be also summarized separately by SOC and treatment period for each sequence group. Fisher's exact test will be used for sequence comparison by visits.

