17. SAFETY OUTCOMES

All outputs for safety outcomes will be based on the Safety Analysis Set. All safety output will be presented by treatment sequence group at each treatment period.

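### SAP 17.1.1.3 leaves treatment period out of its repeat-event rule, although its ADR table is presented by treatment period

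*SAP*

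**What the plan says.** SAP 17.1.1.3 (Adverse Drug Reaction) has a repeat-event sentence that runs across a page break: "If a patient reports the same AE more than once within that SOC/ PT, the AE with the worst case relationship to", continuing with "study medication will be used in the corresponding relationship summaries". Its next sentence describes the section's only named output: "Frequency and percentage of patients having adverse drug reactions will be presented by treatment sequence group, treatment period, SOC and PT".

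The two sections before it are worded differently. On severity, SAP 17.1.1.1 says "If a patient reports a TEAE more than once within that SOC/ PT/Treatment period, the AE with the highest severity grade will be used". On relationship, SAP 17.1.1.2 says "If a patient reports the same AE more than once within that SOC/ PT/Treatment period, the AE with the worst case relationship to study medication" is the one to use.

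Protocol 9.9.4 sets the general rule: "The incidence of TEAEs will be summarized to include only one occurrence of a PT per patient per treatment period". SAP 17 adds: "All safety output will be presented by treatment sequence group at each treatment period". SAP 3.3, which lists changes to the analysis from the protocol, mentions no change to how adverse events are counted.

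**The concern.** A rule that keeps one record per patient per preferred term cannot correctly fill a table that is split by period when the event returns in another period. One of the two periods loses that patient.

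This matters because patients pass through three periods and the by-period safety tables are meant to show what happens after each transition. Protocol 8.3.2.4 lists response to de-challenge and re-challenge among the factors for judging causality, so a second occurrence may be rated more related than the first. A worst-case rule applied across periods would then keep the later record and remove the earlier one. If the ratings are equal, the SAP has no tie-break, and the period that keeps the event is left to the programmer. SAP 17.1 also plans Fisher's exact tests for each treatment period across the adverse event categories, so a misplaced count could enter a planned comparison.

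**Working it through.** The plan gives no figure on this point, so there is nothing to reproduce. The check is a comparison of the counting rules, followed by simple counts.

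**Step 1: the rules side by side**

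| Place | Repeats are collapsed within | Period named in the rule? |
|---|---|---|
| Protocol 9.9.4 | patient, PT (and SOC), period | yes |
| SAP 17.1.1.1 (severity) | patient, SOC/PT, period | yes |
| SAP 17.1.1.2 (relationship) | patient, SOC/PT, period | yes |
| SAP 17.1.1.3 (ADR) | patient, SOC/PT | no, but the table is by period |

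**Step 2: the literal rule applied to one patient with the same PT in periods 1 and 3**

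| Rating in period 1 / period 3 | Counted per period | Counted by the literal 17.1.1.3 rule |
|---|---|---|
| possible / probable | periods 1 and 3 | period 3 only |
| probable / possible | periods 1 and 3 | period 1 only |
| possible / possible | periods 1 and 3 | one period; the SAP does not say which |

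The same happens for any pair of periods and in either sequence group. It requires that both occurrences are ADRs with the same preferred term.

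**Step 3: size per patient.** Each sequence group has about 69 patients (protocol 9.1, SAP 3.1). One patient removed from one period changes that period's incidence for the term by 1/69 = 0.0145, about 1.4 percentage points.

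**Step 4: range for a whole group.** The documents give no ADR or recurrence rate, so both are assumed here. Let n = 69, let p be the share of patients with a given ADR in each of periods 1 and 3, and let r be the share of the period 1 patients who have it again in period 3.

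- Counted per period, periods 1 and 3 together: 2np
- Counted by the literal rule: 2np − npr
- Share of counts lost: npr / 2np = r/2

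| Assumed p | Per period | r = 0 | r = 25% | r = 50% | r = 100% |
|---|---|---|---|---|---|
| 5% | 6.90 | 6.90 | 6.04 | 5.18 | 3.45 |
| 10% | 13.80 | 13.80 | 12.08 | 10.35 | 6.90 |
| Share lost | – | 0% | 12.5% | 25% | 50% |

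The loss runs from nothing to half of the combined count and depends only on recurrence. If the rule is programmed within period, the loss is zero throughout.

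**The case against.** The best defence is that the sentence, read to its end, concerns only the relationship summaries. Possible, probable and definite events all qualify as ADRs, so counting patients with an ADR in a period needs no worst-case selection, and the ADR table has its own sentence that names the period. Protocol 9.9.4, the general statement in SAP 17 and the silence of SAP 3.3 also point to counting within period.

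Much of this stands. It makes a drafting slip the likeliest explanation. It does not clear the text. If the sentence governs the relationship summaries, it contradicts SAP 17.1.1.2, which sets a different rule for those summaries. If it governs the ADR table, it removes recurrences from that table. Either way one section must change.

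A reader might infer more than the documents support:

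- **That the SAP collapses ADRs over the whole study.** It does not say so. This is inferred from a missing term.
- **That recurrence on return to the test product is specifically hidden.** The literal rule would affect both sequence groups and every pair of periods.
- **That the event disappears from the report.** Events the investigator rates as related still show by period under SAP 17.1.1.2. Allergic reactions are summarised by period under 17.1.5, and the listings cover all adverse events.
- **That the ADR and related-event tables ought to be identical.** Section 17.1.1.2 uses the investigator's rating, whereas 17.1.1.3 also admits events that the sponsor considers related. The two can differ legitimately. For the same reason, 17.1.1.2 is not a complete backup for a recurrence that only the sponsor considers related.
- **That a significant difference would be lost.** An example can be built: 6/69 versus 0/69 gives a two-sided Fisher p of 0.028, and removing four recurrences leaves 2/69 versus 0/69, p = 0.50. It needs assumed counts and a tie-break that the SAP does not contain. For a row counting patients with any ADR, it also needs every ADR of those four patients in that period to repeat an already counted term.

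**Conclusion.** The point holds as a minor inconsistency. The repeat-event rule in SAP 17.1.1.3 lacks the treatment period that its two neighbouring sections and the protocol include, while its own output is by period. If programmed literally and applied to the ADR table, it would remove about 1.4 percentage points from one period's incidence of a term for each patient with the same ADR in two periods. That figure rests on 69 patients per group. The total effect cannot be stated, because it depends on a recurrence rate that the documents do not give. If programmed within period, there is no effect. The primary HbA1c analysis, its population and its decision rule are not affected.

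**What to change.** In SAP 17.1.1.3, replace *within that SOC/ PT* with *within that SOC/PT/Treatment period*. Each period's ADR count then includes every patient with an ADR in that period, in line with SAP 17.1.1.1, 17.1.1.2 and protocol 9.9.4. No cross-period tie-break is then needed. The cost is one phrase in the SAP, and the programming follows the neighbouring tables. No analysis is lost and there is no downside.

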17.1.2. TEAEs LEADING TO DISCONTINUATION OF STUDY MEDICATION

TEAEs leading to permanent discontinuation of study medication will be identified by using the Treatment sequence group withdrawn field in the CRF under “Action taken with IMP/ study medication” or recorded as “Yes” in the CRF under “Did the AE cause the subject to discontinue from the study?”.

For TEAEs leading to discontinuation of study medication, summaries of incidence rates (frequencies and percentages) by SOC and PT will be prepared for each treatment period.

17.1.3. SERIOUS ADVERSE EVENTS

Serious adverse events (SAEs) are those events recorded as “Serious” on the Adverse Events page of the (e) CRF. A summary of serious TEAEs by SOC and PT will be prepared for each treatment period.

17.1.4. ADVERSE EVENTS LEADING TO DEATH

TEAEs leading to death are those events which are recorded as “Fatal” on the Adverse Events page of the (e) CRF. A summary of TEAEs leading to death by SOC and PT will be prepared for each treatment period.

17.1.5. LOCAL OR SYSTEMIC ALLERGIC REACTION

TEAE incidence of both local and systemic allergic reaction will be summarized by SOC and treatment sequence group for each treatment period. A separate listing will also be produced which include only events of local or systemic allergic reaction.

17.2. LABORATORY EVALUATIONS

Results from the central laboratory will be included in the reporting of this study for Hematology, Blood Chemistry, lipid profile and Urinalysis. A list of laboratory assessments to be included in the outputs is included in the protocol.

Presentations will use SI Units provided the conversion factors and SI Units are shared by sponsor.

Quantitative laboratory measurements reported as “< X”, i.e. below the lower limit of quantification (BLQ), or “> X”, i.e. above the upper limit of quantification (ULQ), will be converted to X for the purpose of quantitative summaries, but will be presented as recorded, i.e. as “< X” or “> X” in the listings.

Week 52 result from MYL-GAI-3001 trial will be considered as baseline.

The following summaries (descriptive statistics for quantitative measurements and frequency and percentage for qualitative measurements) will be provided for laboratory data:

Document:	\\JEEDC-NAS01A\Biosdata\Mylan\INSULIN_GLARGINE\UXA25824\Biostatistics\Documentation\SAP		
Author:	[name] and [name]	Version Number:	Final V1.0
		Version Date:	[27JUL2016]

Template No: CS_TP_BS016 – Revision 3
Effective Date: 01May2012

Reference: CS_WI_BS005

Copyright © 2012 Quintiles Transnational Corp. All rights reserved.

The contents of this document are confidential and proprietary to Quintiles Transnational Corp. Unauthorized use, disclosure or reproduction is strictly prohibited.

- Actual and change from baseline by visit (for quantitative measurements).
- Incidence of abnormal values according to normal range criteria.
- Shift from baseline according to normal range criteria (for quantitative measurements and/or categorical measurements).
- Shift from baseline according to markedly abnormal criteria (for quantitative measurements and/or categorical measurements).
- Listing of patients meeting markedly abnormal criteria.
- Change from baseline of laboratory measurements will be analyzed using MMRM with model terms of region, treatment sequence group, visit, treatment sequence group-by-visit interaction as fixed effects, and baseline value as covariate. The descriptive statistics for actual measurement and change from baseline along with treatment sequence group comparison will be performed at scheduled visits. LS means for each treatment sequence group and associated standard errors will be derived. Differences in LS means will be calculated and associated 2-sided 95% confidence intervals (p-value, as required) will be provided. These will be derived from the calculation of Type III sum-of-square and LS Means from MMRM model.
- The percentage of patients in categories such as abnormal/non-clinically significant and abnormal/clinically significant will be analyzed using Fisher's exact test. P-value for the two-sided test will be presented.

17.2.1. LABORATORY REFERENCE RANGES AND MARKEDLY ABNORMAL CRITERIA

Quantitative laboratory measurements will be compared with the relevant laboratory reference ranges in SI units and categorized as:

- Low: Below the lower limit of the laboratory reference range.
- Normal: Within the laboratory reference range (upper and lower limit included).
- High: Above the upper limit of the laboratory reference range.

17.3. ECG EVALUATIONS

Results from the central ECG (Electrocardiogram) Reading Centre will be included in the reporting of this study.

Week 52 result from MYL-GAI-3001 trial will be considered as baseline.

Frequency and percentage of overall assessment of ECG (investigator's judgment) will be presented.

The percentage of patients in categories such as abnormal/non-clinically significant and abnormal/clinically significant will be summarized and treatment sequence group comparison will be performed using Fisher's exact test. The p-value will be presented for the same.

17.4. VITAL SIGNS

The following vital signs measurements will be reported for this study:

Document:	\\IEEDC-NAS01A\Biosdata\Mylan\INSULIN_GLARGINE\UXA25824\Biostatistics\Documentation\SAP	Version Number:	Final V1.0
Author:	[name] and [name]	Version Date:	[27JUL2016]

Template No: CS_TP_BS016 – Revision 3
Effective Date: 01May2012

Reference: CS_WI_BS005

Copyright © 2012 Quintiles Transnational Corp. All rights reserved.

The contents of this document are confidential and proprietary to Quintiles Transnational Corp. Unauthorized use, disclosure or reproduction is strictly prohibited.

- Sitting Systolic Blood Pressure (mmHg)
- Sitting Diastolic Blood Pressure (mmHg)
- Sitting Pulse Rate (bpm)
- Respiratory Rate (breaths/min)
- Temperature (°C)
- Weight (kg)

The following summaries will be provided for all above vital signs parameters data:

- Actual and change from baseline by visit
- Incidence of markedly abnormal values
- Listing of patients meeting markedly abnormal criteria

Change from baseline (week 52 result from MYL-GAI-3001 trial) of vital sign measurements will be analyzed using MMRM with model terms of region, treatment sequence group, visit, treatment sequence group-by-visit interaction as fixed effects, and baseline value as covariate. The descriptive statistics including actual measurement and change from baseline along with treatment sequence group comparison will be performed at scheduled visits for each period. LS means for each treatment sequence group and associated standard errors will be derived. Differences in LS means will be calculated and associated 2-sided 95% confidence intervals (p-value, as required) will be provided. These will be derived from the calculation of Type III sum-of-square and LS Means from MMRM model.

The percentage of patients in categories such as potentially clinically significant will be analyzed using Fisher’s exact test. P-value for the two-sided test will be presented. Descriptive statistics will also be provided as summary tables.

17.4.1. POTENTIAL CLINICALLY SIGNIFICANT CHANGES

Potential clinically significant changes in vital signs measurements will be identified in accordance with the following predefined markedly abnormal criteria

Variable	Unit	Low	High
SBP	mmHg	≤ 90 mmHg AND change from baseline ≤ -20 mmHg	≥ 160 mmHg AND change from baseline ≥ 20 mmHg
DBP	mmHg	≤ 50 mmHg AND change from ≤ -15 mmHg	≥ 100 mmHg AND change from baseline ≥ 15 mmHg
Heart rate	Bpm	≤ 50 bpm AND change from baseline ≤ -15 bpm	≥ 120 bpm AND change from baseline ≥ 15 bpm

Document: \\JEEDC-NAS01A\Biosdata\Mylan\INSULIN_GLARGINE\UXA25824\Biostatistics\Documentation\SAP
 Author: [name] and [name] Version Number: Final V1.0
 Version Date: [27JUL2016]

Template No: CS_TP_BS016 – Revision 3
 Effective Date: 01May2012

Reference: CS_WI_BS005

Variable	Unit	Low	High
Body temperature	°C	NA	≥ 38.3 °C AND change from baseline ≥ 1.1 °C
Weight	Kg	percentage change from baseline ≤ - 7.0 %	percentage change from baseline ≥ 7.0 %

17.5. PHYSICAL EXAMINATION

Listings will be generated for all physical examination tests.

17.6. OTHER SAFETY ASSESSMENTS

17.6.1. DEVICE SAFETY ASSESSMENT

The device safety assessment will use responses to investigator-administered device questionnaires, and incidence of device-related AEs.

The total incidence of device-related safety events will be summarized with each treatment sequence group both for device-related TEAEs and for events related to device complaints or failures. For device-related TEAEs, two categories will be summarized for each treatment sequence group: needle-related TEAEs such as pain, bruise, and bleeding; and other device-related TEAEs, such as hyperglycemia or hypoglycemia. For confirmed device-related malfunction or failures, incidence will be listed and summarized for each treatment sequence group.

If there are sufficient events of any category, a Fisher exact test will be performed for treatment sequence group comparison. The p-value for the corresponding two-sided test will be presented.

Number and percentage of subjects with device complaints, device complaints leading to dosing error and device complaints leading to an adverse event will be presented.

17.6.2. IMMUNOGENICITY PROFILES ANALYSES

Following parameters will be summarized for immunogenicity.

- Total Insulin Antibodies
 - Percent Binding (%B/T, Continuous outcome)
 - Positive/Negative (Categorical outcome)
- Cross Reactive Insulin Antibodies
 - Percent Binding (%B/T, Continuous outcome)
 - Positive/Negative (Categorical outcome)

Document:	\\JEEDC-NAS01A\Biosdata\Mylan\INSULIN_GLARGINE\UXA25824\Biostatistics\Documentation\SAP	Version Number:	Final V1.0
Author:	[name] and [name]	Version Date:	[27JUL2016]

Template No: CS_TP_BS016 – Revision 3
 Effective Date: 01May2012

Reference: CS_WI_BS005

Copyright © 2012 Quintiles Transnational Corp. All rights reserved.

The contents of this document are confidential and proprietary to Quintiles Transnational Corp. Unauthorized use, disclosure or reproduction is strictly prohibited.

- Insulin(Drug) Specific Antibody
 - Percent Binding (%B/T, Continuous outcome)
- Anti-HCP
 - Positive/Negative (Categorical outcome)

Immunogenicity profiles with continuous variables (% binding) will be analyzed using the MMRM method for each assay, similar to change from baseline efficacy analyses. The model will include the terms region, treatment sequence group, visit, treatment sequence group-by-visit as fixed effects, and baseline value as covariate. The treatment sequence group difference and 95% confidence intervals will be constructed using the model at scheduled visits. In case the normal distribution assumption is severely violated, then non-parametric analysis will be performed using Wilcoxon rank-sum test for treatment sequence group comparison, Hodges Lehmann's estimator will be used to compute the median difference between the treatment sequence groups and the corresponding 95% confidence interval. Safety population will be used for ADA continuous variables. Immunogenicity profiles with dichotomous outcomes will be summarized with frequency and percentage at scheduled visits for each assay. Treatment sequence group comparison will be performed using Fisher's exact test. P-value for the two-sided test will be presented.

Correlation analyses of insulin cross-reactive antibodies with clinical factors such as HbA1c and insulin doses will be performed by treatment sequence group along with graphics to explore relationship of insulin antibodies with such factors for each assay method used. Additionally, mean (\pm SD) and median (IQR) for actual measurements by visit will also be presented.

Regression plots will be produced to assess the consistency of results obtained between the two assay types, and the regression plots will be produced for Total Insulin Antibody, Cross Reactive Insulin Antibody and Insulin (Drug) Specific Antibody by treatment sequence group.

The incidence of patients with increase over 10% cross reacting antibody increase in both assays, of HbA1c over 0.2% increase and insulin dose increase at any visit will also be summarized descriptively (for categorical measures) together to explore treatment sequence group difference.

An individual data listing will be provided for the patients with increase over 10% cross reacting antibody increase in both assays, of HbA1c over 0.2% increase and insulin dose increase at Week 12, 24 and 36.

The observed and Change values of HbA1c, Insulin dose, Cross reactive antibodies (Both assays) Fasting blood glucose, Subject's age, Duration of diabetes and Adverse events reported will be presented in the listing.

Presence of anti-HCP antibodies in samples from patients will be assessed using a validated immunoassay method. The results will be presented as positive or negative from anti-HCP antibodies based on the samples that HCP assay was done. Frequency and percentage of presence of anti-HCP antibodies will be presented at scheduled visits by treatment sequence group. The p-value from Fisher's exact test will be presented to test the difference between the treatment sequence groups for scheduled visits.

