Patients who successfully completed 52 weeks in MYL-GAI-3001 will be eligible to participate in the extension study. Patients exposed to different types of insulins may have different immune responses following exposure to trial drug. This confounding effect will be minimized as only patients who have been on Lantus® (besides mealtime insulin lispro) for the last 52 weeks prior to the randomization will be included in the trial.

Patients on Lantus® during MYL-GAI-3001 will be randomized to Mylan’s insulin glargine or Lantus® for 12 weeks; following which, those on Mylan’s insulin glargine will be switched to Lantus®, and those on Lantus® will continue on Lantus® for another 12 weeks. During the consecutive 12-week comparative treatment periods, diabetes treatment will be either maintained or further controlled (if needed) by titrating the dose of Lantus® or Mylan’s insulin glargine, if necessary. After the 24 weeks of treatment, those patients who were randomized to Mylan’s insulin glargine and had a switch to Lantus® will undergo an additional switch to Mylan’s insulin glargine for an additional 12 weeks to complete the third treatment period. Those patients who are on Lantus® since the start of the study and did not have any switch will continue on Lantus® for another 12 weeks to complete the third treatment period.

All patients will continue on insulin lispro for the entire duration of the study. After completion of the 36 week treatment, patients will go back to the approved medications (as prescribed earlier, prior to their participation in the MYL-GAI-3001 study) on their own and will be followed up for safety for another 4 weeks (Mylan will not provide any medications during the safety follow-up period). The 36 to 40 week safety data will be captured. This 4-week follow-up visit is to confirm that patients are safe on the prescribed medications.

Twelve weeks exposure is considered adequate to assess the efficacy with respect to HbA1c, as well as to compare the safety between the treatment groups. If switching from Lantus® to Mylan's insulin glargine or from Mylan's insulin glargine to Lantus® have an impact on the efficacy or the safety, a discernible difference in efficacy or safety parameters is expected versus the group of patients who are continuing on Lantus® throughout.

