### ***9.9.2. Immunogenicity Profiles Analyses***

Continuous immunogenicity variables such as cross-reacting antibodies percent binding will be analyzed using the MMRM ANCOVA model, similar to the primary and secondary efficacy analyses. The model will include the fixed, categorical effect of region and

sequence group, visit, sequence group-by-visit interaction and the other as fixed effect terms region, and baseline value as covariates. The p-value for sequence difference and 95% confidence interval will be constructed. If the normal distribution assumption is severely violated, then non-parametric analysis will be performed using Wilcoxon rank-sum test for sequence comparison.

Descriptive statistical summaries for actual measurements and change from baseline will be displayed by visit for each sequence group. For categorical variables such as ADA positive and negative, frequency table will be presented by visit for each period for each sequence. Fisher's exact test will be used for sequence comparison by visit.

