2.2. SECONDARY OBJECTIVES

To compare treatment sequence group of Mylan's insulin glargine to Lantus®, at 36 weeks, when administered in combination with mealtime insulin lispro with respect to:

1. Change in basal insulin dose per unit body weight (U/Kg/day).
2. Immunogenicity: incidence and change from baseline in the relative levels of ADA, incidence and change from baseline in the relative levels of anti-HCP antibodies.
3. Rate of hypoglycemic events per 30 days; and occurrence of hypoglycemia
4. Occurrence of local reactions, systemic reactions and other adverse events.
5. Change in fasting plasma glucose from baseline.
6. Change in 8-point (self-monitored blood glucose) SMBG profile from baseline
7. Device related safety assessment.

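### ADA incidence is a secondary objective, but the only categorical between-group test of ADA and anti-HCP is per-visit prevalence, which ignores week 0 antibody status

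*SAP*

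**What the plan says.** SAP 2.2 lists "incidence and change from baseline in the relative levels of ADA" among the secondary objectives, and the same pair for anti-HCP antibodies. Protocol 2.1 does the same. Incidence and level are therefore two separate targets.

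For positive/negative results, SAP 17.6.2 says "Immunogenicity profiles with dichotomous outcomes will be summarized with frequency and percentage at scheduled visits for each assay" and adds Fisher's exact test between the sequence groups. Protocol 9.9.2 agrees: "frequency table will be presented by visit for each period for each sequence", and "Fisher's exact test will be used for sequence comparison by visit". Neither document defines conversion, boosted or treatment-emergent ADA, or a cumulative post-baseline incidence. Neither uses baseline status in the categorical comparison.

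For levels, SAP 17.6.2 says "Immunogenicity profiles with continuous variables (% binding) will be analyzed using the MMRM method for each assay, similar to change from baseline efficacy analyses". The model has "treatment sequence group-by-visit as fixed effects, and baseline value as covariate". This covers total, cross-reactive and drug-specific antibody. The same section plans a descriptive summary of patients with a rise of more than 10% in cross-reacting antibody in both assays. It is presented together with HbA1c rises above 0.2% and insulin dose increases at any visit, with listings at weeks 12, 24 and 36.

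Anti-HCP appears in SAP 17.6.2 as positive/negative only, again tested by visit. Protocol 7.3.2 expects many patients to carry such antibodies already and plans to follow relative levels through the ECL response of the screening assay.

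On prior exposure, Protocol 1.1 admits "only patients who have been on Lantus® (besides mealtime insulin lispro) for the last 52 weeks prior to the randomization". Protocol 7.3 takes the randomization sample, which comes from MYL-GAI-3001, as the antibody baseline.

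**The concern.** The percentage positive at a visit is a prevalence. After a year on the reference glargine plus lispro, some patients may well be antibody-positive at week 0. Such a patient who does not change counts as positive at all 12 post-baseline visits, whichever group he or she is in. A patient who turns positive after a switch and later reverts is scattered over separate visit tables and never counted once as a new positive. A patient already positive whose antibody level rises stays in the same cell.

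Protocol 1.1 expects a discernible difference in safety parameters if switching has an effect. The categorical antibody comparison should be able to show one. As planned, the incidence half of a stated objective has no matching between-group analysis, and a responder definition chosen after the data are seen would carry little weight in an open-label trial.

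**Working it through.** **The plan's own figure.** The only power statement in the documents is 90% for HbA1c equivalence (Protocol 9.1, SAP 3.1: limits ±0.4%, SD 0.61%, no true difference, 69 per group, 10% without usable data).
- Evaluable per group: 69 × 0.9 = 62.1, taken as 62.
- Power = 2Φ(0.4 / (0.61 × √(2/62)) − 1.96) − 1 = 90.9%, or 90.3% with a t approximation.

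The figure reproduces. It says nothing about ADA, but it supplies the 62 per group used below.

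**Dilution.** Let b be the proportion positive at week 0 and c the probability that a baseline-negative patient converts. If baseline-positives stay positive, prevalence at a visit is b + (1 − b)c. The between-group difference in prevalence is then (1 − b)(c_switch − c_Lantus).

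**Assumptions.** The documents give neither b nor c. I take c = 25% in the switching group and 5% in the Lantus group, and vary b. Power is exact for the two-sided Fisher test at 0.05, by full binomial enumeration.

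| b | Per-visit prevalence | Difference | Power, prevalence (62 per group) | Power, conversion among baseline-negatives (n per group) |
|---|---|---|---|---|
| 0% | 25% vs 5% | 20 points | 86% | 86% (62) |
| 20% | 40% vs 24% | 16 points | 41% | 75% (50) |
| 40% | 55% vs 43% | 12 points | 23% | 59% (37) |
| 60% | 70% vs 62% | 8 points | 12% | 37% (25) |
| 80% | 85% vs 81% | 4 points | 6% | 9% (12) |

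The pattern does not hinge on the chosen rates. At b = 20/40/60/80%:
- 30% vs 5%: prevalence 59/35/17/7%, conversion 90/78/55/16%.
- 40% vs 10%: prevalence 74/48/25/10%, conversion 93/82/59/23%.

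**Boosting only.** If switching raises levels only in patients already positive, the percentage positive is the same in both groups and the Fisher test rejects at its null rate, about 3%. A combined endpoint (converted or boosted) keeps all 62 per group in the denominator. If its true rates were 25% vs 5%, power would be 86%.

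**Cost of an any-visit rule.** With 12 post-baseline samples and an assumed independent false-positive rate f per sample, a true negative is called converted with probability 1 − (1 − f)^12. This is 1 − 0.99^12 = 11% at f = 1%, and 1 − 0.95^12 = 46% at f = 5%. The values of f are assumptions too.

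**The case against.** The strongest reply is that the plan does more than tabulate positives, and this largely stands. A reader might infer that no analysis uses baseline antibody data, or that no patient-level rise is ever counted. The documents do not support either reading. The MMRM on % binding adjusts for baseline, runs per assay and per visit, and has a Wilcoxon and Hodges-Lehmann fallback. Protocol 7.3.1 treats specific binding as comparable to a titer. That is a proper test of the level part of the objective. The over-10% summary is a within-patient, any-visit count.

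Neither closes the incidence gap. The MMRM compares group means, so a marked rise in a few patients can be lost, and the rank-based fallback shares this weakness. The over-10% summary is descriptive and limited to cross-reactive antibody in both assays. It is tied to HbA1c and dose increases, and does not say whether 10% is absolute or relative.

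A reader might also infer that the plan as a whole masks a switching effect, or that the by-visit Fisher test is biased. That goes too far. Randomization balances baseline positives in expectation, so the test is valid; it is inefficient for this question. The by-visit tables also show timing after each switch, which one 36-week count hides.

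The power figures rest on assumed rates, and the comparison is not strictly like for like. The same 25% and 5% serve both a single-visit prevalence and an any-visit conversion, although any-visit counting accumulates false positives. The 62 per group borrows the HbA1c loss, whereas the SAP uses the safety population for the continuous ADA variables. At 80% baseline positivity, conversion alone gains almost nothing (9% against 6%).

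**Conclusion.** The point holds for the categorical analysis. The planned test measures prevalence, whereas the objective names incidence. The loss follows from the algebra: the difference in new positives is multiplied by (1 − baseline positivity), and boosts are invisible to this test. Under the stated assumptions, power at 20 to 60% baseline positivity is 41% falling to 12%, against 75% falling to 37% for conversion among baseline-negatives. These figures show a direction and a range; no estimate for this trial is possible without the baseline rate.

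For ADA the shortfall is partial, because the level half of the objective is tested. Anti-HCP is less protected: a high pre-existing rate is expected, the objective includes change in level, and the SAP analyses positive/negative only, with no analysis of the ECL response. Immunogenicity is secondary, so the HbA1c equivalence conclusion is unaffected. The change should be made, but the trial's main result does not depend on it.

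**What to change.** In SAP 17.6.2, define treatment-emergent ADA per assay, for total and cross-reactive ADA, as either of:
- (a) Conversion: negative at week 0 and positive at a post-baseline visit up to week 36, with a sensitivity version requiring positivity at two or more visits to limit accumulated false positives.
- (b) Boost: positive at week 0 with a rise in % specific binding above a limit fixed before database lock. Reconcile this limit with the existing over-10% rule and state whether it is absolute or relative.

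Compare the 36-week incidence of (a), and of (a or b), between sequence groups by Fisher's exact test, with the difference and its 95% CI, and also show it by period. Keep per-visit positivity as descriptive prevalence, split by baseline status.

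For anti-HCP, add conversion among baseline-negatives and a baseline-adjusted analysis of the ECL response foreseen in Protocol 7.3.2. The ECL analysis matters more here, since few patients may be negative at week 0.

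The cost is SAP wording, a few tables and one boost limit to agree with the laboratory. No new samples are needed. The any-visit rule will still collect some false positives in both groups, which the two-visit version limits but does not remove.
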